**Table 3. Prohibited and Rescue Medications**

Rescue/supportive medication/class of drug:	Usage:
Concomitant medications or treatments (e.g., acetaminophen or diphenhydramine) deemed necessary by the Investigator to provide adequate prophylactic or supportive care, except for those medications identified as “prohibited” as listed above	To be administered as prescribed by the Investigator
Best supportive care (including antibiotics, nutritional support, growth factor support, correction of metabolic disorders, optimal symptom control, and pain management)	Should be used when necessary for all patients. Additional RT is strongly discouraged outside of the RT required on this study.

## **8. STUDY PROCEDURES**

### **8.1 Schedule of study procedures**

Before study entry, throughout the study, and following study drug discontinuation, various clinical and diagnostic laboratory evaluations are outlined. The purpose of obtaining these detailed measurements is to ensure adequate safety and tolerability assessments. Clinical evaluations and laboratory studies may be repeated more frequently if clinically indicated. The Schedules of Study Assessments during the screening and treatment period is provided following the Protocol Synopsis.

#### **8.1.1 Screening Phase**

Screening procedures will be performed up to 28 days before Day 1, unless otherwise specified. All subjects must first read, understand, and sign the IRB/REB/IEC-approved ICF before any study-specific screening procedures are performed. After signing the ICF, completing all screening procedures, and being deemed eligible for entry, subjects will be enrolled in the study. Procedures

and imaging studies that are performed prior to the signing of the ICF and are considered standard of care may be used as screening assessments if they fall within the 28-day screening window. Pre-treatment tumor biopsy should be performed within the 28-day screening window. It is preferred that laboratory tests required for screening or entry be performed within 10 days prior to receiving the first dose of durvalumab.

The following procedures will be performed during the Screening Visit:

- Informed Consent
- Review of eligibility criteria
- Medical history and demographics
- Complete physical exam
- ECOG Performance Status
- Vitals signs, weight and height
- 12-lead ECG (in triplicate [2-5 minutes apart])
- Tumor biopsy (if archival tumor is not available)
- Review of prior/concomitant medications
- CT scan chest, abdomen, pelvis
- Clinical laboratory tests for:
  - Hematology (see Table 7)
  - Clinical chemistry (see Table 8)
  - TSH
  - Coagulation (PT, PTT, INR)
  - Creatinine Clearance
  - Serum pregnancy test (for women of childbearing potential only)
  - Hepatitis serologies
  - Urinalysis (see Table 9)
  - CA 19-9

### **8.1.2 Treatment Phase**

Procedures to be conducted during the treatment phase of the study are presented in the Schedule of Study Assessments. Screening procedures performed within 72 hours of Cycle 1 Day 1 (C1D1) do not need to be repeated on C1D1.

### **8.1.3 End of Treatment**

End of treatment is defined as the last planned dosing visit within the 12-month dosing period. For subjects who discontinue durvalumab prior to 12 months, end of treatment is considered the last visit where the decision is made to discontinue treatment. All required procedures may be completed within  $\pm 7$  days of the end of treatment visit. Repeat disease assessment is not required if performed within 28 days prior to the end of treatment visit.

Assessments for subjects who have completed durvalumab treatment and achieved disease control, or have discontinued durvalumab due to toxicity in the absence of confirmed progressive disease are provided in APPENDIX B.

Assessments for subjects who have discontinued durvalumab treatment due to confirmed PD are presented in APPENDIX C.

All subjects will be followed for survival until the end of the study regardless of further treatments, or until the sponsor ends the study.

## **8.2 Description of study procedures**

### **8.2.1 Medical history and physical examination, electrocardiogram, weight and vital signs**

Findings from medical history (obtained at screening) and physical examination shall be given a baseline grade according to the procedure for AEs. Increases in severity of pre-existing conditions during the study will be considered AEs, with resolution occurring when the grade returns to the pre-study grade or below.

Physical examinations will be performed on study days noted in the Schedule of Study Assessments.

A complete physical examination will be performed and will include an assessment of the following (as clinically indicated): general appearance, respiratory, cardiovascular, abdomen, skin, head and neck (including ears, eyes, nose and throat), lymph nodes, thyroid, musculo-skeletal (including spine and extremities), genital/rectal, and neurological systems and at screening only, height.

ECGs are required during screening, prior to starting study treatment on Cycle 1 Day 1, at 16 weeks or at least one time after starting study treatment, at the end of treatment, as well as at any other time point when clinically indicated.

ECGs recorded during the screening period will be obtained in triplicate (with 2-5 minute lag time between each); ECGs recorded during the treatment phase will be single tracing. All 12-lead ECGs should be recorded while the subject is in the supine position. A 12-lead ECG will be recorded for all subjects on study days noted in Section 8.1. The same method of assessment should be used throughout the study. Twelve-lead ECGs will be obtained after the subject has been resting in a supine position for at least 5 minutes in each case. On Day 1 and Week 16, ECGs will be recorded within an hour prior to start of infusion and at least one time point 0 to 3 hours after the infusion.

Vital signs (temperature, blood pressure, pulse rate, and respiratory rate) will be measured on study days noted in the Schedule of Assessments. On durvalumab treatment days, vital signs will be measured within an hour prior to start of durvalumab administration, at 30 minutes during the infusion ( $\pm 5$  minutes), at the end of infusion ( $+ 5$  minutes), and at 30 minutes ( $\pm 5$  minutes) and 60 minutes ( $\pm 5$  minutes) post-infusion. If the infusion takes longer than 60 minutes, then blood pressure and pulse measurements should follow the principles described here, or more frequently if clinically indicated. For subsequent doses (at dose levels of 10 mg/kg or less), the 1-hour observation period will not be required unless a subject experiences an infusion-related reaction.

### **8.2.2 Clinical laboratory tests**

Laboratory tests for screening or entry should be performed within 10 days prior to the first dose of treatment. After Cycle 1, pre-dose laboratory procedures can be conducted up to 72 hours prior to dosing. Results must be reviewed by the investigator or qualified designee and found to be acceptable prior to each dose of trial treatment. If screening laboratory values are not acceptable for study enrollment per the inclusion/exclusion criteria, then subjects may not be enrolled; laboratory tests may be repeated and the subject may be enrolled if the values are acceptable per the study protocol. Otherwise subjects whose laboratory values are not deemed acceptable per the study protocol may seek off-protocol therapy. After study enrollment, the investigator should evaluate laboratory values that are outside of the reference range and a determination should be made whether this represents an AE.

Clinical Study Protocol

Investigational Drug Substance: MEDI4736

Study Number **ESR 15 11078**

Edition Number **1.09**

Date **01 Feb 2018**

The following clinical laboratory tests will be performed (see the Schedule of Study Assessments, Appendix B and Appendix C for the timepoints of each test):

- Coagulation parameters: Activated partial thromboplastin time and International normalised ratio to be assessed at baseline and as clinically indicated
- Pregnancy test (female subjects of childbearing potential only)
  - Urine human chorionic gonadotropin
  - Serum beta-human chorionic gonadotropin (at screening only)
- Thyroid Stimulating Hormone
  - free T3 and free T4 only if TSH is abnormal
- Other laboratory tests
  - Hepatitis A antibody, hepatitis B surface antigen, hepatitis C antibody
  - HIV antibody
  - CA 19-9

**Table 4. Hematology Laboratory Tests**

---

Basophils	Mean corpuscular volume
Eosinophils	Monocytes
Hematocrit	Neutrophils
Hemoglobin	Platelet count
Lymphocytes	Red blood cell count
Mean corpuscular hemoglobin	Total white cell count
Mean corpuscular hemoglobin concentration	

---

**Table 5. Clinical chemistry (Serum or Plasma) Laboratory Tests**

---

Albumin	Glucose
Alkaline phosphatase	Lactate dehydrogenase
Alanine aminotransferase	Lipase
Amylase	Magnesium
Aspartate aminotransferase	Potassium
Bicarbonate	Sodium
Calcium	Total bilirubin a
Chloride	Total protein
Creatinine	Urea or blood urea nitrogen, depending on local practice
Gamma glutamyltransferase b	Uric acid

---

a If Total bilirubin is  $\geq 2 \times \text{ULN}$  (and no evidence of Gilbert's syndrome) then fractionate into direct and indirect bilirubin

b At baseline and as clinically indicated

**Table 6. Urinalysis Testsa**

Bilirubin	pH
Blood	Protein
Glucose	Specific gravity
Ketones	Colour and appearance

a Microscopy should be used as appropriate to investigate white blood cells and use the high power field for red blood cells

### **8.2.3 Patient reported outcomes (PRO)**

PROs will be measured by the EORTC QLQ-30 and EORTC QLQ-PAN26 questionnaires. Subjects will complete both questionnaires starting with the EORTC QLQ-30 questionnaire first. The questionnaires will be completed by all subjects prior to study therapy, every 2 weeks until Week 8, and then every 4 weeks thereafter. PRO questionnaires will be administered to the subject by a clinical research staff member who is knowledgeable about both questionnaires although the same research staff member is not required to be present each time. Both questionnaires will be administered on paper and this data will then be entered into the electronic study database by designated clinical research staff.

#### **8.2.3.1 EORTC QLQ-C30**

The EORTC QLQ-30 is a widely used cancer-specific health-related QOL assessment tool.(Quinten, Martinelli et al. 2014) It contains 30 items and measures 5 functional dimensions (physical, role, cognitive, social, emotional), 6 single items (appetite loss, constipation, dyspnea, financial impact, sleep disturbance, diarrhea), 3 symptom items (fatigue, pain, nausea/vomiting) and a global health and QOL scale.

### **8.2.3.2 EORTC QLQ-PAN26**

The EORTC QLQ-PAN26 is one of the most widely used tools for measuring QOL in pancreatic cancer patients.(Fitzsimmons, Johnson et al. 1999, Hurt, Mukherjee et al. 2015) It comprises 26 questions assessing pain, dietary changes, jaundice, altered bowel habit, emotional problems related to pancreatic cancer, and other symptoms (cachexia, indigestion, flatulence, dry mouth, taste changes).

## **8.3 Tissue/Blood Collection, and Storage Guidelines**

### **8.3.1 Biomarker/Pharmacodynamic Tissue sampling and evaluation methods**

#### **PD-L1 Testing**

PD-L1 testing will be performed by immunohistochemistry using assay developed by Ventana using SP263 antibody.

#### **Sample collection for PD-L1 testing**

- The preferred tumor sample for the determination of a patient's PD-L1 status is the one taken following the completion of the most recent prior line of therapy. Samples taken at this time reflect the current PD-L1 status of the tumor and considered clinically most relevant.
- The preferred sample for PD-L1 testing is less than or equal to 3 months old. In cases where a sample less than 3 months old was not available, patients will undergo a new biopsy if considered clinically appropriate by their treating physician.
- Samples should be collected via a core needle of 18 gauge or larger or be collected by an incisional or excisional tumor biopsy. Where institutional practice uses a smaller gauge needle, samples should be evaluated for tumor cell quantity (i.e. >100 tumor cells) to allow for adequate PD-L1 immunohistochemistry analyses.

- When obtaining fresh tumor tissue is not clinically appropriate, archival samples may be utilized that were obtained within the past 3 years. When archival samples are used to assess PD-L1 status, the age of the sample / date of collection should be captured.
- Samples submitted for PD-L1 testing should be formalin fixed and embedded in paraffin. Samples from fine needle aspirates (FNA) or decalcified bone are not appropriate for PD-L1 analysis.

### **Sample data collection for PD-L1 testing**

The following fields of data should be collected from the site/institution collecting and if, indicated shipping of the samples:

- Patient identifier (unique identifier)
- Specimen identifier (written on the specimen)
- Site identifier (e.g., Miami Cancer Institute)
- Specimen collection date
- Type of specimen submitted
- Quantity of specimen
- Date of sectioning
- Archival of fresh tumor
- Tumor type
- Primary tumor location
- Metastatic tumor location (if applicable)
- Fixative

**The following fields of data should be collected from PD-L1 testing laboratory:**

- Are the negative and positive controls stained correctly
- Is the H&E material acceptable
- Is morphology acceptable
- Total percent positivity of PD-L1 in tumor cells
- PD-L1 status (positive, negative or NA) in tumor cells

- Total percent positivity of PD-L1 in infiltrating immune cells

### **Sample processing and if indicated submission process for PD-L1 testing**

#### Preparing Stored samples for testing

- Where samples already exist, they should be retrieved from the storage location. These blocks should undergo quality review, prior to evaluation or shipment. Where it is not possible or indicated to ship the block to a testing laboratory, unstained slides should be prepared from the paraffin-embedded tumor sample block (described below) prior to evaluation or shipment.

#### Preparing newly acquired samples for PD-L1 testing

- If patients are undergoing a biopsy procedure that provides the option to submit newly acquired samples, this sample should be used to determine PD-L1 expression level. Where clinically acceptable, a minimum of 2 core biopsies should be collected and processed to FFPE in a single block. The provision of 2 cores is advised in order to provide sufficient tissue for PD-L1 assessment.
- It is recommended that core needle tumor biopsies are collected using an 18 gauge or larger needle and the process should be image-guided. Excisional or incisional samples are also adequate. If this is not per the institutions normal practice and a smaller gauge needle is used then the number of cores collected should be increased to allow sufficient material for successful PD-L1 testing (>100 tumor cells) and embedded in the same block. If available, a single excisional biopsy of at least 4 mm in diameter may substitute for all core biopsies.

#### Fixation of biopsy samples for PD-L1 testing

- Previously frozen tissue is not acceptable for processing to FFPE for PD-L1 testing. To fix newly acquired tissue, place immediately (within 30 min of excision) into an adequate volume of 10% v/v neutral buffered formalin (NBF). Samples should remain in fixative for 24 – 48 hours at room temperature.

- It is vital that there is an adequate volume of fixative relevant to the tissue (at least a 10 volume excess) and that large specimens (if any) are incised prior to fixation to promote efficient tissue preservation.

#### Embedding in paraffin for PD-L1 testing

- An overnight processing schedule into paraffin wax is recommended
- Below is the suggested routine overnight processing schedule:

#### Storage of tumor blocks for PD-L1 testing

- FFPE blocks should be stored at ambient temperature and protected from light until shipment by courier at ambient temperature. FFPE blocks are stable under these conditions for an indefinite period.

#### Quality control of samples to be used for PD-L1 testing

- Tissue should be assessed by the site pathologist prior to PD-L1 testing.
- Each sample should be reviewed for:
  - Adequate fixation
  - Good preservation of morphology
  - Presence of tumor tissue
  - Histopathology consistent with indication
  - Greater than 100 tumor cells are required to determine PD-L1 expression level – tumor cell content must be reviewed prior to testing in order for PD-L1 obtain a valid result.

#### Sectioning instructions

- Unstained slides should be prepared from the paraffin-embedded tumor sample block as described below:

Clinical Study Protocol

Investigational Drug Substance: MEDI4736

Study Number **ESR 15 11078**

Edition Number **1.09**

Date **01 Feb 2018**

- A minimum of 5-10 x 4 micron ( $\mu\text{m}$ ) thick, unstained sections should be provided for PD-L1 testing
- A new disposable microtome blade must be used for each block to prevent contamination between Slides are stable under these conditions for 6 months.
- patient samples
- Apply one section per slide to positively-charged Superfrost glass slides
- The sections should be dried overnight between room temperature and 37°C. Do not dry sections at temperatures above 37°C.

Sections should be stored at ambient temperature and protected from light until use or shipment to testing lab by courier at ambient temperature. It is recommended that slides are cut freshly prior to PD-L1 testing and they are used within 90 days of being cut to obtain PD-L1 expression level.

Once prepared for shipping, specimens should be sent for centralized PD-L1 testing to:

Department of Pathology  
Baptist Hospital of Miami  
[name]  
[name]  
E-mail: [[contact]](mailto:[contact])

### **8.3.2 Blood samples for correlative studies**

Blood for correlative studies should be drawn at the time points detailed in the Schedule of Study Assessments (Pre-Treatment on Day 1, and on Days 15, 29, and 52). These specimens should be transported to the Protocol Support Laboratory at Miami Cancer Institute (See section 8.3.4). A 4 teaspoon blood sample will be required to fill two 10mL Sodium Heparin tubes. Sodium heparin tubes for this study are available from the Protocol Support Laboratory. Blood sample tubes to be inverted several times immediately after the blood draw. The tubes may be transported to the Protocol Support Laboratory at ambient Temperature. It is preferable for the research blood to arrive to the Protocol Support Laboratory within 1-2 hours of the blood draw.

Clinical Study Protocol  
Investigational Drug Substance: MEDI4736  
Study Number **ESR 15 11078**  
Edition Number **1.09**  
Date **01 Feb 2018**

### **8.3.3 Future biomedical research**

If a patient consents to the optional future biomedical research, then at Pre-treatment, and on Days 1 and 52 the blood draw will include an additional 2 teaspoons of blood to fill one 10mL Sodium Heparin tube as the correlative study blood draw. This sample is sent to the Protocol Support Laboratory. See the Schedule of Study Assessments. Blood sample tube to be inverted several times immediately after the blood draw and the tube may be transported to the Protocol Support Laboratory at ambient Temperature.

### **8.3.4 Blood Sample Processing and Storage**

Specimens should be transported to the following address:

Protocol Support Laboratory  
Miami Cancer Institute  
[name]  
[name]  
Email: [[contact]](mailto:[contact])

Please contact the Protocol Support Laboratory; [name] at [[contact]](mailto:[contact]) or [[contact]](mailto:[contact]) at the time of courier transport.

Samples should be processed by the lab within 30 minutes of collection. Once in the lab, blood will be diluted 1:1 with phosphate buffered saline (PBS) and then layered onto an equal volume of Lymphocyte Separation Media. The blood will then be centrifuged at 1500g for 30 minutes (no break) at room temperature within one hour of collection. The plasma will be removed, aliquoted, and labeled with the study number (GCC 1598), subject's study number, "plasma", volume and date, and frozen at -80C. The cells or "buffy coat" will then be removed, and placed into a new 15 cc conical tube. Ten ml of ice cold PBS will be added to the cells in the tube and then the tube will be inverted 5 times and centrifuged at 350g for 10-15 min at 4C. The tube will be gently inverted to pour off supernatant—the pellet should not be disturbed. Once the tube is upright the pellet will be dislodged by gently tapping the tube. Ten ml of ice cold phosphate buffered saline (PBS) will be added. The tube will be inverted five times, a 100ul aliquot

removed for counting, then centrifuged one last time at 350g for 10-15 min at 4C. Cells will be counted by trypan blue exclusion. After centrifugation, supernatant will be aspirated and the cells will be re-suspended to yield cells at 10-20 million cells per ml in freezing media (95% FBS / 5%DMSO). The viably frozen cells will be labeled with the study ID (GCC1598), subject's study ID, site ID, date and number of cells. The cells should be placed in a [name], if possible, in a -80C freezer.

### 8.3.5 Estimate of volume of blood to be collected

The total volume of blood that will be drawn from each subject in this study is as follows:

**Table 7. Volume of Blood to Be Drawn From Each Subject**

Assessment	Sample volume (mL)	No. of samples	Total volume (mL)
Safety	Clinical chemistry	10	18
	Hematology	10	18
Liver function tests	5	12	60
Coagulation parameters	5	1	5
Correlative studies (PBMCs, MDSCs)	20	5	100
Future Biomedical Research	10	3	30
Total for duration of study			555 mL = 112.6 teaspoons = 2.3 cups “about 2 cups”

### 8.3.6 Withdrawal of informed consent for donated biological samples

If a subject withdraws consent to the use of donated samples, the samples will be disposed of/destroyed, and the action documented. As collection of the biological samples is an integral part of the study, then the subject is withdrawn from further study participation.

The Principal Investigator:

- Ensures that biological samples from that subject, if stored at the study site, are immediately identified, disposed of /destroyed, and the action documented
- Ensures the laboratory(ies) holding the samples is/are informed about the withdrawn consent immediately and that samples are disposed/destroyed, the action documented and the signed document returned to the study site
- Ensures that the subject is informed about the sample disposal.

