f If screening laboratory assessments are performed within 3 days prior to Day 1 they do not need to be repeated at Day 1. Results for safety bloods must be available and reviewed before commencing an infusion. Gamma glutamyltransferase tested at Screening, Day 1 and as clinically indicated.

g Free T3 and free T4 will only be measured if TSH is abnormal. They should also be measured if there is clinical suspicion of an adverse event related to the endocrine system.

h Urinalysis performed at Screening, Day 1, every 4 weeks and as clinically indicated.

Clinical Study Protocol

Investigational Drug Substance: MEDI4736

Study Number **ESR 15 11078**

Edition Number **1.09**

Date **01 Feb 2018**

- i Coagulation tests: prothrombin time, APTT and INR – only performed at Screening and as clinically indicated.
- j CT scans preferably with IV contrast, are collected during screening (for baseline) and as close to and prior to initiation of study treatment. Timing of on-treatment (follow-up) CT scans is every 8 weeks ( $\pm$  1 week) until PD or off-study. Response according to RECIST 1.1 criteria (CR, PR) requires a confirmatory scan preferably at the next regularly scheduled imaging visit and no earlier than 4 weeks after the prior assessment of CR, PR, or SD. Confirmation of PD for patients who are deemed clinically stable by the Investigator should be acquired preferably at the next regularly scheduled imaging visit and no earlier than 4 weeks after the prior assessment of PD.
- l For AEs/SAEs reported during prescreening additional information such as medical history and concomitant medications may be needed.
- m Blood (approximately 4 teaspoons =20mL) will be drawn for correlative studies. Tumor and additional blood (approximately 2 teaspoons = 10mL) for future biomedical research (FBR) is optional, but patient consent must be obtained prior to sample collection. If a patient does not consent for FBR then only blood for correlative studies will be drawn.
- n Tumor tissue for PD-L1 analysis from fresh biopsy or archival tissue sample must be obtained before treatment begins. Biopsy or archival tissue must be obtained by core needle or excisional biopsy. If the subject signs the Future Biomedical Research (FBR) consent, any leftover tissue that would ordinarily be discarded at the end of the main study will be retained for FBR.

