## **4. SUBJECT SELECTION**

### **4.1 Inclusion criteria**

For inclusion in the study subjects must fulfill all of the following criteria:

1. Written informed consent and any locally-required authorization (e.g., HIPAA in the USA, EU Data Privacy Directive in the EU) obtained from the subject prior to performing any protocol-related procedures, including screening evaluations
2. Age  $\geq$  18 years at time of study entry.
3. Eastern Cooperative Oncology Group (ECOG) performance status of 0 or 1.
4. Life expectancy of  $\geq$ 12 weeks as estimated by the investigator.
5. Biopsy-proven metastatic pancreatic adenocarcinoma with progression through standard first-line chemotherapy. Chemotherapy given as part of prior chemoradiation in the setting of non-metastatic pancreatic cancer does not count as a line of therapy.
6. At least 3 radiographically distinct pancreatic cancer lesions that are measurable by RECIST 1.1 criteria, including 2 that are (eligible) for RT
7. No lesion that would receive RT  $>$ 7 cm in greatest dimension.
8. Subjects must consent to all study procedures described in the protocol including radiographic evaluation and repeated blood draws.
9. Adequate normal organ and marrow function as defined below:
  - Hemoglobin  $\geq$  9.0 g/dL

- Absolute neutrophil count (ANC)  $\geq 1.5 \times 10^9/L$  ( $\geq 1500$  per  $\text{mm}^3$ )
- Platelet count  $\geq 100 \times 10^9/L$  ( $\geq 100,000$  per  $\text{mm}^3$ )
- Serum bilirubin  $\leq 1.5 \times$  institutional upper limit of normal (ULN). This will not apply to subjects with confirmed Gilbert's syndrome (persistent or recurrent hyperbilirubinemia that is predominantly unconjugated in the absence of hemolysis or hepatic pathology), who will be allowed only in consultation with their physician.
- AST (SGOT)/ALT (SGPT)  $\leq 2.5 \times$  institutional upper limit of normal unless liver metastases are present, in which case it must be  $\leq 5 \times$  ULN
- Serum creatinine  $\text{CL} > 40$  mL/min by the Cockcroft-Gault formula (Cockcroft and Gault 1976) or by 24-hour urine collection for determination of creatinine clearance:

Males:

$$\text{Creatinine CL (mL/min)} = \frac{\text{Weight (kg)} \times (140 - \text{Age})}{72 \times \text{serum creatinine (mg/dL)}}$$

Females:

$$\text{Creatinine CL (mL/min)} = \frac{\text{Weight (kg)} \times (140 - \text{Age})}{72 \times \text{serum creatinine (mg/dL)}} \times 0.85$$

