### **11.2.2 Primary Efficacy Analysis**

All patients entered are evaluable with respect to the efficacy endpoints. The primary endpoint is PFS. The benchmark median PFS for metastatic pancreatic adenocarcinoma who have progressed through first line chemotherapy is 3 months (Oettle, Riess et al. 2014).

The expected accrual rate is 18 patients per year and we add a 12-months maturation period after completing accrual. Patients enrolled during the continuous toxicity monitoring portion of the trial will all be included in the phase II efficacy analysis. All patients will be analyzed according to a strict intention-to-treat principle.

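### Section 8.3.6 ends study participation when consent to donated samples is withdrawn, with no exception for the optional research samples and no provision for continued PFS and survival follow-up

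*Combined protocol and SAP*

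**What the plan says.** Section 8.3.6 deals with a subject who withdraws consent to the use of donated samples. The samples are destroyed and this is documented. The section then gives a reason, "As collection of the biological samples is an integral part of the study", and a consequence, "then the subject is withdrawn from further study participation". It does not distinguish between types of sample.

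Other sections do distinguish:

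- **Optional samples.** Footnote m to the Schedule of Study Assessments says that tumor and additional blood "for future biomedical research (FBR) is optional, but patient consent must be obtained prior to sample collection". On refusal it says: "If a patient does not consent for FBR then only blood for correlative studies will be drawn". Section 8.3.3 uses the same language: "If a patient consents to the optional future biomedical research".
- **Required samples.** Inclusion criterion 8 in Section 4.1 reads: "Subjects must consent to all study procedures described in the protocol including radiographic evaluation and repeated blood draws". Section 8.3.2 schedules the correlative blood, and footnote n requires PD-L1 tissue before treatment starts.

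On follow-up, Sections 4.3 and 8.1.3 say that all subjects are followed for survival. Sections 9.1.1 and 9.1.3 continue tumor assessments in patients taken off durvalumab for reasons other than confirmed progression. The withdrawal-of-consent paragraph in Section 4.3 says that such a subject receives no more study drug and no more study observation. On analysis, Section 11.2.2 states: "All patients will be analyzed according to a strict intention-to-treat principle".

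**The concern.** There are two problems.

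First, the stated reason does not fit every sample that the rule reaches. A patient who declines FBR on Day 1 stays in the trial. A patient who agrees and later changes their mind is, as 8.3.6 is written, taken out of it. Nothing in the protocol explains the difference, and it makes an optional choice costly to reverse.

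Second, 8.3.6 does not say what happens to outcome follow-up. A site could read it together with the withdrawal-of-consent paragraph in Section 4.3 and stop scans and contact. The patient would then be censored for PFS and overall survival because of a decision about samples. Since that decision is the patient's own, it may be related to how they are faring, and the censoring may be informative. The trial is single-arm with 39 patients and PFS as its primary endpoint, so it should not lose outcome data for a reason that the wording could avoid.

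**Working it through.** **1. The passages side by side**

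| Situation | Consequence in the protocol | Where |
|---|---|---|
| Patient declines FBR at entry | Stays on study; only correlative blood is drawn | Schedule of Study Assessments, footnote m |
| Patient withdraws consent to donated samples, type not specified | Withdrawn from further participation | 8.3.6 |
| Patient withdraws consent (general) | No further drug or observation | 4.3 |
| Any subject | Followed for survival | 4.3, 8.1.3 |
| Patient off durvalumab without confirmed progression | Tumor assessments continue | 9.1.1, 9.1.3 |

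The first two rows treat the same optional sample differently according to when the patient says no. The second row does not say which of the last three applies.

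**2. What happens in the analysis**

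Section 11.2.2 makes every patient entered evaluable, and Section 11.4 censors at last contact. (For PFS it speaks of patients alive with no evidence of disease; I read this as no documented progression.) A patient removed under 8.3.6 therefore stays in the analysis set with shortened follow-up. The set itself changes only if the patient leaves before the first efficacy scan and is replaced under Section 4.4.

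**3. The plan's own sample size**

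Inputs from Sections 11.2.2 and 11.3: one-sided 5% test, 80% power, median PFS 3 against 4.5 months, exponential survival, 18 patients per year, 26 months of accrual, 12 months of further follow-up.

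- Events needed, taking the historical median as fixed: (1.645 + 0.842)² / (ln 1.5)² = 37.6.
- Hazard at a 4.5-month median: λ = ln 2 / 4.5 = 0.154 per month.
- Probability of an observed event: 1 − [exp(−12λ) − exp(−38λ)] / (26λ) = 0.961.
- Patients needed: 37.6 / 0.961 = 39.1, which agrees with the stated 39. Accrual agrees too: 26 × 1.5 per month = 39.
- Expected events from 39 patients: 39 × 0.961 = 37.5.

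**4. What a lost patient costs**

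Power is approximately Φ(√events × ln 1.5 − 1.645). The documents give no withdrawal rate, so the number lost, k, is an assumption shown over a range. The middle column takes events = (39 − k) × 0.961. The right-hand column takes (39 − k/2) × 0.961.

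| k of 39 | Power if each contributes no event | Power if each loses half of its information |
|---|---|---|
| 0 | 79.9% | 79.9% |
| 1 | 79.0% | 79.4% |
| 2 | 78.0% | 79.0% |
| 3 | 77.1% | 78.5% |
| 4 | 76.0% | 78.0% |

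Each patient who contributes no event costs about one percentage point.

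**The case against.** The best defence is that 8.3.6 was written for the required samples. Its reason suits the correlative blood and the PD-L1 tissue, and consent to repeated blood draws is an entry condition. It does not suit FBR, so a sensible site might not apply it there. Footnote n also mentions a separate FBR consent, which may have its own withdrawal terms; the consent form is not among the documents reviewed. This shows that the intent may have been narrower. It does not supply the missing exception: the section refers to donated samples without qualification and comes after the FBR section.

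Three stronger readings are tempting, and the documents do not support them:

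- **That the rule breaks intention-to-treat.** It does not. The patient stays in the analysis set, censored at last contact, unless replaced under Section 4.4. What is at risk is follow-up.
- **That observation definitely ends.** Section 8.3.6 does not say so. The inference depends on the general withdrawal paragraph in Section 4.3, while Sections 4.3 and 8.1.3 promise survival follow-up for everyone and Sections 9.1.1 and 9.1.3 continue scans after durvalumab is stopped. The passages need reconciling; the loss is possible, not established.
- **That the design has no slack, because 37.6 events are needed and 37.5 expected.** That comparison shows only that 39 patients were chosen to meet the target. Early leavers may be replaced, and patients censored later still contribute follow-up time.

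**Conclusion.** The point holds as a minor defect of wording with a simple remedy. As written, 8.3.6 removes a patient from the study for reversing a choice that the protocol calls optional. It also leaves unclear whether PFS and survival follow-up continue after any withdrawal of sample consent. The possible harm is avoidable, perhaps informative, censoring of the primary endpoint and of overall survival.

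Its size is probably small. One patient contributing no PFS event takes power from 79.9% to about 79.0%, and two take it to 78.0%. These figures rest on the plan's exponential model, a fixed 3-month benchmark and an assumed number of losses. They describe precision only; the documents give no basis for estimating any bias from informative censoring. The stated sample size, significance level and power are unaffected.

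**What to change.** Amend Section 8.3.6 and the matching consent text to say two things:

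1. Withdrawing consent for the optional FBR samples leads only to destruction of those samples and no further FBR sampling. It does not in itself end study participation.
2. After any withdrawal of sample consent, PFS and survival follow-up continue unless the patient also withdraws consent to follow-up.

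The amendment need not waive the required correlative sampling. Whether that sampling remains a condition of participation, and whether study treatment is affected, is for the sponsor to reconcile with Sections 4.1 and 4.3.

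The cost is a sentence or two in the protocol and the corresponding consent wording. It needs no new type of visit or data and no change to the sample size.
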